13.4 Primary Objective #2

To characterize the safety of the Integrated Diagnostic Medication Intervention Strategy in resolving the subject risk.

13.4.1 Hypothesis

There is no statistical hypothesis for this objective.

13.4.2 Endpoint Definition

Once initiated, the Integrated Diagnostic Medication Intervention Strategy will be regarded as being safe if all the following criteria are met:

- The Integrated Diagnostic Medication Intervention applied to an episode is not terminated due to safety issues;

NOTE: Safety issues include hypotension with/without patient contact and weight loss with patient contact.

- And, the Integrated Diagnostic Medication Intervention applied to an episode has not caused treatment-related adverse events (as adjudicated by the CEC).

13.4.3 Performance Requirements

There are no performance requirements for this objective

13.4.4 Rationale for Performance Criteria

Rationale for performance criteria is not applicable for this objective.

13.4.5 Analysis Methods

Similar to the effectiveness endpoint of Integrated Diagnostic Medication Intervention Strategy, the safety endpoint of Integrated Diagnostic Medication Intervention Strategy is a correlated binary outcome with 1=safe and 0=not safe. It will be analyzed using a generalized linear model with GEE method. The safety rate and its 95% CI will be calculated based on the log of odds estimated using GEE.

13.4.6 Determination of Patients/Data for Analysis

All subjects who have received the Integrated Diagnostic Medication Intervention.

13.4.7 Sample Size

The same estimates on the precision of measuring effectiveness rate of Integrated Diagnostic Medication Intervention Strategy under different scenarios illustrated in Table 19 and Figure 9 above are applicable to the safety rate as well. Again, using the first row in Table 19 as an example, a total of 70 independent episodes with Integrated Diagnostic Medication Intervention produces a two-sided 95% CI with an actual width of 0.225 when the observed proportion of having safe treatment among those episodes is 0.7.

13.5 Ancillary Objective

To characterize the occurrence of Heart Failure (HF) events in the study subjects.

13.5.1 Hypothesis

There is no statistical hypothesis for this objective

13.5.2 Endpoint Definition

The endpoint of this objective is the number of HF events per subject, as adjudicated by CEC.

13.5.3 Analysis Methods

The number of HF events will be summarized using frequency and percentage, and stratified by the implementation status of Integrated Diagnostic Medication Intervention (1=have ever received the intervention, 0=have never received the intervention). A Poisson regression model will be used to analyze the number of HF events, adjusting for the implementation of

Integrated Diagnostic Medication Intervention. The fit of the Poisson regression model will be checked. If over dispersion is a concern, a negative binomial model may be considered. It is important to note, that those who have received the Integrated Diagnostic Medication Intervention might be sicker when compared to subjects who have never received the Integrated Diagnostic Medication Intervention, and therefore, are more likely to have HF events. Thus, the number of HF events before and after the intervention will be summarized using descriptive statistics for the subjects who have received such intervention.

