- e. **Combination variable:** The final variable that is input into the integrated diagnostic algorithm combines pacing and arrhythmia related information. Specifically, one of the components of this variable is substantial decrease (>8%) in CRT pacing, which is associated with high HF events.¹⁷ A decline in CRT pacing can occur because of rapid conduction during AF. Thus, mean ventricular rate \geq 90 bpm and atrial fibrillation (AF) burden \geq 6 hours/day and shocks delivered to Ventricular Fibrillation/Ventricular Tachycardia (VT/VF) are also components of this variable.

Each of the five variables input into the Heart Failure Risk Status - Integrated Diagnostics Algorithm (ID1.0 HFRS-ID) has a prognostic value for HF. Combining these variables into a single HF risk metric yields a prognostic indicator that is better than each of the individual components alone because these variables capture slightly orthogonal information (e.g. while decrease impedance is an indicator of elevated pulmonary pressure, HRV is an indicator of autonomic imbalance), and hence add to provide a better overall snapshot of patient status. Our model development data indicate that a patient with a risk score in the 'high' group were 10 times more likely to have an Heart Failure Hospitalization (HFH) in the next 30 days compared with 'low' risk patients.¹⁰ A patient with 'medium' risk status is at 2x higher risk of hospitalization in the next 30 days.¹⁰

While a high performance diagnostic is necessary for effective HF patient management, previous clinical trials have shown that diagnostic information alone is not sufficient to improve patient management. For example, the COMPASS-HF¹⁸ and REDUCE-HF¹⁹ trials that provided clinically relevant estimated pulmonary artery (PA) pressure measurements to physicians for HF management did not show statistically significant difference in HF based outcomes between PA pressure management arm and control arm. This lack of outcome improvement was attributed to lack of clinical actions in response to changes in PA pressure.

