6.5 F) Ensuring Subject Safety

6.5.1 Criterion for not initiating or continuing with a PRN Intervention

At the time of subject contact, (following the CareLink transmission and subject having been stratified as High risk), the ISCC nurse will make sure that the subject is not hypotensive based on the blood pressure measurement for the day of contact. If the subject has not yet transmitted the blood pressure measurement for the day of contact, the nurse will instruct the subject to obtain blood pressure measurement while on the phone. If the subject's systolic blood pressure is below 85 mmHG with associated hypotensive symptoms, the intervention will not be initiated. Additionally in the instance that the subject is unable or unwilling to provide a blood pressure measurement, the subject will be assessed for potential hypotensive symptoms – if positively reported, the medication intervention will not be initiated. ISCC will send an 'Interim Patient Report' to the subject's investigator noting the reason for not initiating PRN intervention. Subject's investigator will be required to further evaluate the subject, take necessary actions, and document them in eCRFs.

To ensure subject safety while a PRN intervention is underway, the subject's will be asked to provide a blood pressure and weight daily. If a predefined, physician specified, patient specific, safety threshold is crossed for either weight or blood pressure the subject will be

contacted by ISCC nurse. The nurse will telephonically evaluate the subject for symptoms known to suggest that intervention may not be safe (Table 11). If any one of the two symptoms is present, PRN will be stopped and the investigator will be sent an 'Exception Report' to assist with further subject follow-up (see Appendix B: ISCC Reports to Physician for an example of this report). The ISCC nurse will make one attempt to establish the contact with subject to evaluate subject symptoms to potentially stop PRN intervention. If the nurse is unable to establish the subject contact, a report will be sent to the investigator and/or phone call will be made to the site to notify that values were outside threshold(s).

Table 11: Safety Thresholds for Cessation of Medication Intervention (PRN)

PRN Cessation and Safety Threshold(s):			
Hold/Discontinue PRN Diuretic use if telephonically assessed to have met Weight or BP threshold and Symptom(s):			

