7.7.1 OptiVol Fluid Index Verification

The subject's OptiVol Fluid Index on the day of screening must be below prescribed threshold to be eligible.

If the subject's OptiVol Fluid Index is above threshold, then the subject can return at a later date for OptiVol reevaluation. If the subject does not return for a later OptiVol reading, they shall be exited and reported as a screen failure.

If at the time of screening the OptiVol Fluid Index is equal to or greater than threshold and is deemed to be an artifact by the investigator and the subject is otherwise stable and euvolemic, a reference reset can be performed at the time of the baseline visit and the patient shall stay in the study and proceed to the next step.

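### The before/after HF-event count in PRN recipients is cut at a High-risk alert, with unequal time on each side, so it can show more events after a PRN that does nothing or helps

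*Protocol*

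**What the plan says.** The ancillary objective is to characterize HF events. Protocol 13.5.2 defines it: "The endpoint of this objective is the number of HF events per subject, as adjudicated by CEC". Protocol 13.5.1 adds: "There is no statistical hypothesis for this objective".

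Protocol 13.5.3 first plans a Poisson comparison of subjects who ever and never received the intervention. It then warns that "those who have received the Integrated Diagnostic Medication Intervention might be sicker when compared to subjects who have never received" it, and draws the consequence that, for recipients, "the number of HF events before and after the intervention will be summarized using descriptive statistics". SAP 7.9.3.3 repeats the text. Neither document defines the length of the two periods, a person-time denominator, or which PRN is the cut-point when a subject has several. Neither says whether HF events before enrollment count as before.

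Three other parts of the protocol bear on the cut-point:
- Section 6.5.1 places the call at which a PRN may start "following the CareLink transmission and subject having been stratified as High risk".
- Section 2 says that a subject in the High group was "10 times more likely to have an Heart Failure Hospitalization (HFH) in the next 30 days" than one in the Low group. It gives 2x for Medium, read here as relative to Low.
- Section 7.7.1 requires that the "OptiVol Fluid Index on the day of screening must be below prescribed threshold to be eligible", with an exception for a crossing judged to be an artifact.

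**The concern.** Comparing recipients with themselves removes stable differences between patients, which is the problem the plan names. It brings in a timing problem instead. The date that divides before from after is chosen because the subject has just been rated High. The alert window of every PRN therefore falls almost entirely in the after period. The before period runs from a visit at which the fluid index normally had to be under threshold, up to that rating.

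A second problem adds to this. The plan counts events, and recipients are followed for longer after the first PRN than before it.

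The study's findings are meant to guide a pivotal study. A table with more HF events after the PRN than before could be read as harm or failure when it mainly shows when PRNs are given.

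**Working it through.** **The plan's own figure.** Protocol Table 18: 43 + 62 + 63 + 40 + 25 = 233 crossings. 0.45 × 233 = 104.85, or about 105 needing a PRN. Both reproduce.

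**Inputs from the documents.** 233/200 = 1.165 crossings per subject-year; 45% of subjects with no crossing in a year (55% have at least one); 45% of crossings leading to a PRN; 18 months of enrollment and closure at month 30, so 12 to 30 months of follow-up.

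**Assumptions not in the documents.** Crossings are negative binomial with that mean and that share of zeros. Accrual is uniform. The HF hazard is constant except in the 30 days after each PRN. In units of the Low risk, R is the hazard in those 30 days and m the hazard at other times. R = 10 is the High score and R = 2 is Medium. R = 6 is an even mix, (10 + 2)/2, because Protocol 6.3.1 also rates a subject High on a Medium transmission plus symptoms or weight gain.

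**Time on each side.** In simulation, 48% of subjects receive a PRN, with on average 8.5 months before the first and 13.2 after it. With no difference in hazard at all, the count ratio is 13.2/8.5 = 1.55. The 30-day windows after PRNs take up f = 0.133 of the after time.

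**Formulas.**
- No PRN effect: rate ratio = 1 + f(R/m − 1). Example: 1 + 0.133 × 9 = 2.20.
- Hazard halved for the 30 days only: replace R by R/2. Example: 1 + 0.133 × 4 = 1.53.
- Halving that lasts through all later time: half the no-effect value.
- Count ratio = rate ratio × 1.55.

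| R | m | No effect: rate (count) | Halved 30 days: rate (count) | Lasting halving: rate (count) |
|---|---|---|---|---|
| 10 | 1 | 2.20 (3.41) | 1.53 (2.38) | 1.10 (1.71) |
| 6 | 1 | 1.67 (2.59) | 1.27 (1.97) | 0.83 (1.29) |
| 2 | 1 | 1.13 (1.76) | 1.00 (1.55) | 0.57 (0.88) |
| 10 | 2 | 1.53 (2.38) | 1.20 (1.86) | 0.77 (1.19) |

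**If the periods were equal 30-day windows.** With R = 10 halved, the ratio is 5/m: 5.0 at m = 1 and 2.5 at m = 2.

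**If before meant the 6-month history taken at baseline.** Assume a Low risk of 1% per 30 days and that 20% of recipients had an event in that history. Six months after a PRN that halves a 10-fold risk gives 0.01 × (5 + 5) = 0.10 events with a 30-day halving, or 0.01 × (5 + 2.5) = 0.075 with a lasting one. The ratios are 0.50 and 0.375, the opposite direction. With 10% instead of 20% they are 1.00 and 0.75.

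**Removing the 30-day windows.** Time before the first PRN against later time outside the windows gives m/m = 1.00 with no PRN effect. It also gives 1.00 when the PRN halves the 30-day hazard.

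**The case against.** The strongest reply is that this is one descriptive summary under an ancillary objective, in a single-arm feasibility study that disclaims showing improvement. The plan promises no ratio, test or causal reading. HF events during and within 14 days after an intervention are already judged episode by episode in Primary Objective 1. All of that is true. It limits the weight of the point, but it does not make the table readable.

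A reader might go further and infer that the summary must show more HF events after the PRN even if the PRN halved HF risk. The documents do not support that:
- The rate ratio is 1.00 at 2 times halved, and falls below 1 in several cases with a lasting halving.
- Low-level risk before the alert is an assumption. A fluid index under threshold is not a Low risk score, which combines several inputs. Eligibility selects for raised BNP, a recent crossing or a recent HF event.
- High alerts that lead to no PRN can fall in the before period, and repeated contact attempts (6.4.1.2) can put early alert days there too. If every crossing without a PRN also carried 10 times the risk, the no-effect ratio would fall from 2.2 to about 1.8.
- Counting pre-enrollment history could reverse the direction. Adjudication by the events committee and event collection from consent suggest it is not counted, but the text does not say so.

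Nor does the plan claim that the before/after summary is free of bias. It only offers it as the response to the severity concern.

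**Conclusion.** The point holds as a conditional one. Followed as written, the summary can show more HF events after the PRN when the PRN does nothing or helps. With no effect and Low-level risk before the alert, the rate ratio is about 2.2, 1.7 or 1.1 at 10, 6 or 2 times the risk, and the count ratio about 3.4, 2.6 or 1.75. With a 10-fold risk halved for 30 days the rate ratio is 1.5, or 1.2 if risk before the alert is twice Low.

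Size and direction turn on that earlier risk, the share of PRNs reached through Medium, and how long any effect lasts; the documents give none of these. The 10x and 2x figures are for HF hospitalization, while the endpoint also counts invasive outpatient treatment. No hypothesis, error rate or sample size is affected. The change should be made, but the study does not depend on it.

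**What to change.** In Protocol 13.5.3 and SAP 7.9.3.3, replace the before/after counts for PRN recipients with HF events and person-months in three rows:
- (a) baseline visit to first PRN, excluding pre-enrollment history;
- (b) days 0-30 after any PRN, which is the risk score's own horizon;
- (c) all other time after the first PRN.

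Report all three descriptively and state that no contrast between them estimates the PRN effect. Row (b) reflects the High-alert state. Row (c) against row (a) leaves out the period in which the PRN acts, so it stays at 1.00 in the model above whether or not the PRN works.

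The cost is a wording change in both documents and one derived period variable from PRN, event and follow-up dates. The downside is fewer HF events in each row.

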13.5.4 Determination of Patients/Data for Analysis

All the enrolled subjects who have completed the baseline and programming visit will be included.

13.6 Preliminary Safety Interim Data Analysis

To summarize preliminary safety of PRN intervention.

13.6.1 Hypothesis

There is no statistical hypothesis for this analysis.

13.6.2 Endpoint Definition

The endpoint of this analysis includes any adverse event reported per protocol.

13.6.3 Analysis Methods

The analysis will occur when 10 PRN interventions have been implemented and the last PRN intervention has been followed up for 14 days. Descriptive statistics such as count and percentage will be used. The seriousness and relatedness of adverse events will be based on the CEC adjudication. If an adverse event has not been adjudicated by the CEC by the time of the analysis, study investigators' assessment (if available) will be considered. The primary interest in the relatedness of adverse events includes but is not limited to safety issues leading to termination of PRN interventions, treatment-related adverse events after implementation of PRN interventions, and HF events occurring within 14 days after completion of PRN intervention. Adverse events occurring before and after PRN interventions will be summarized separately.

13.6.4 Determination of Patients/Data for Analysis

All the subjects who have completed the baseline and programming visit by the time of the analysis.

14 DATA AND QUALITY MANAGEMENT

Data will be collected using an electronic data management system for clinical studies. eCRF data will be stored in a secure, password-protected database which will be backed up nightly. Data will be reviewed using programmed and manual data checks. Data queries will be made available to centers for resolution. Study management reports may be generated to

monitor data quality and study progress. At the end of the study, the data will be frozen and will be retained indefinitely by Medtronic.

All records and other information about subjects participating in this study will be treated as confidential. Data will be transferred and processed by Medtronic or a third party designated by Medtronic in a key coded form, unless it's impossible to make it anonymous, for instance, where the patient's name cannot be removed from the data carrier, such as fluoroscopy images.

Procedures in the CIP require source documentation. Source documentation will be maintained at the site. Source documents, which may include, but not limited to, worksheets, patient medical records, lab results, ECGs, programmer printouts, and interrogation files, must be created and maintained by the investigational site team. In some cases, the data reported in the eCRFs may be considered source, as long as there is evidence of it in the subject's record. The eCRF may serve as the primary source for the following data points but is not limited to the list below (refer to the study-specific monitoring plan for complete listing).

The data reported on the eCRFs shall be derived from source documents and be consistent with these source documents, and any discrepancies shall be explained in writing. If applicable, the eCRF may be considered source for the following data collection elements but not limited to:

- Enrollment Notification
 - Site assigned patient reference
- Baseline
 - Administrative Information
 - Cardiac Disease Classification
- Adverse Event eCRF
 - Date study center became aware of event
 - Relatedness of adverse event
- Device Deficiency eCRF
 - Date study became aware of event
- Subject Death
 - Date study became aware of death
 - Relatedness of death
 - System Explant Information
- System Modification
 - Justification for explanted product not being returned to Medtronic

- Deviations

Device data from transmissions will be uploaded to secure servers. Save-to-disk data collected at office visits will be sent to Medtronic. Upon receipt, device data will be maintained with databases and retrieved for analysis and reporting.

The sponsor or a regulatory authority may audit or inspect the study center to evaluate the conduct of the study. The clinical investigator(s)/institution(s) shall allow study related monitoring, audits, IRB review and regulatory inspection by providing direct access to source data/documents.

It has been determined that a data monitoring committee (DMC) would not be appropriate for this feasibility study.

15 WARRANTY/INSURANCE

Warranty information is provided in the product packaging for the commercially released CRT-D device and additional copies are available upon request.

Medtronic maintains appropriate Clinical Trial liability insurance coverage as required under applicable laws and regulations and will comply with applicable local law and custom concerning specific insurance coverage. If required, a Clinical Trial insurance statement/certificate will be provided to the IRB.

16 MONITORING

It is the responsibility of Medtronic to ensure proper monitoring of this clinical study. Trained Medtronic personnel or delegates appointed by Medtronic may perform study monitoring at the study center in order to ensure that the study is conducted in accordance with the CIP, the Clinical Trial Agreement, and applicable regulatory and local requirements. Medtronic, or delegates, must therefore be allowed access to the subjects' case histories (clinic and hospital records, and other source data/documentation) upon request as per the Subject Informed Consent, Research Authorization (where applicable) and Clinical Trial Agreement. The investigator should also be available during monitoring visits.

16.1 Monitoring Visits

Frequency of monitoring visits may be based upon subject enrollment, duration of the study, study compliance, number of adverse events, number of deviations, findings from previous monitoring visits and any suspected inconsistency in data that requires investigation.

Regulatory documents may be reviewed at each study center. Monitoring for the study, including site qualification visits, site initiation visits, interim monitoring visits, and closeout visits, will be done in accordance to the study-specific monitoring plan.

Monitoring visits may be conducted periodically to assess site study progress, the investigator's adherence to the CIP, regulatory compliance including but not limited to

IRB/IRB approval and review of the study, maintenance of records and reports, and review of source documents against subject eCRFs. Monitors review site regulatory and study compliance by identifying findings of non-compliance and communicating those findings along with recommendations for preventative/corrective actions to site personnel. Monitors may work with study personnel to determine appropriate corrective action recommendations and to identify trends within the study or at a particular center.

17 REQUIRED RECORDS AND REPORTS

17.1 Investigator records

The investigator is responsible for the preparation and retention of the records cited below. All of the below records, with the exception of case history records and case report forms, should be kept in the Investigator Site File (i.e., the study binder provided to the investigator) or Subject Study Binder. Electronic CRFs must be maintained and signed electronically within the electronic data capture system during the study. The following records are subject to inspection and must be retained for a period of two years (or longer as local law or hospital administration requires) after product approval or the date on which the investigation is terminated.

- All correspondence between the IRB, sponsor, monitors, FDA or other regulatory agencies, including required reports that pertain to this study
- Subject's case history records, including:
 - Signed and dated informed consent form signed by subject.
 - Observations of adverse events/adverse device effects/device deficiencies
 - Medical history
 - Implant and follow-up data (if applicable)
 - Documentation of the dates and rationale for any deviation from the protocol
- List of investigation sites
- Financial disclosure
- Normal value(s)/range(s) for subject and clinical laboratory test
- Lab certificate (if applicable)
- Disposition Logs including, but not limited to, record of receipt, use, or disposition of investigational software, device serial number, subject ID, date of turning ON and OFF OptiVol Care Alerts
- All approved versions of the CIP and PIC
- Signed and dated Clinical Trial Agreement
- Current curriculum vitae of principal investigators
- Documentation of delegated tasks
- IRB approval documentation. Written information that the investigator or other study staff, when member of the IRB, did not participate in the approval process. Approval documentation must include the IRB composition, where required per local law.

- Regulatory authority notification, correspondence and approval, where required per local law
- Study training records for site staff
- Any other records that FDA and local regulatory agencies require to be maintained (e.g. financial disclosure)
- Final Study Report including the statistical analysis

